12. ADVERSE EVENTS, SERIOUS ADVERSE EVENTS, AND REPORTING

12.1. ADVERSE EVENTS

12.1.1. Definition

An AE is defined as any untoward medical occurrence in a clinical investigation subject administered a pharmaceutical product and which does not necessarily have a causal relationship with the treatment. An AE can therefore be any unfavorable and unintended sign, symptom, or

disease temporally associated with the use of a medicinal (investigational) product, whether or not related to that product. An AE can arise with any use (eg, in combination with another drug), route of administration, formulation, or dose, including an overdose.

Possible AEs associated with TransCon hGH are listed in the Investigator's Brochure or the accompanying Reference Safety Information. The adverse reactions associated with commercially available daily hGH-containing products that may or may not be observed with use of TransCon hGH are:

- Sudden death in pediatric patients with Prader-Willi syndrome; risk factors include morbid obesity, history of upper airway obstruction or sleep apnea, and unidentified respiratory infection
- Intracranial tumors, particularly meningiomas, in teenagers/young adults treated with brain irradiation as children
- Injection site reactions/rashes (as well as rare, generalized hypersensitivity reactions)
- Skin atrophy and lipoatrophy
- **Note:** Rotating the injection site (see Section 9.3) is expected to decrease the risk of skin atrophy or lipoatrophy.
- Headaches
- Glucose intolerance, including impaired glucose tolerance/impaired fasting glucose as well as overt diabetes mellitus
- Intracranial hypertension with papilledema, visual changes, headache, nausea, and/or vomiting
- Fluid retention manifested by edema, arthralgia, myalgia, nerve compression syndromes (including carpal tunnel syndrome/paresthesias)
- Hypothyroidism (central [secondary] hypothyroidism may first become clinically evident or worsen in patients with GHD during hGH treatment)
- Slipped capital femoral epiphysis (occurs more frequently in patients with endocrine disorders or in patients undergoing rapid growth)
- **Note:** Any subject with the onset of a limp or complaints of hip or knee pain should be carefully evaluated for a slipped capital femoral epiphysis.
- Progression of pre-existing scoliosis due to rapid growth (hGH has not been shown to increase the occurrence of scoliosis)

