13. SAFETY MONITORING

The Sponsor will conduct an ongoing review of all trial data, with particular attention given to laboratory findings, AEs, and concomitant medications. Any important safety trends or other findings considered related to the investigational product will be reported to the investigators and to regulatory authorities. In particular, the Sponsor will notify investigators and regulatory authorities of AEs that:

- Fulfill the criteria for SUSARs
- Occur at a meaningfully greater frequency than described in the current Investigator's Brochure or Reference Safety Information

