14.4. STATISTICAL ANALYSES

Baseline and demographic data will be summarized to characterize the study population. Subgroups of interest, such as prior exposure to hGH and age categories, will be determined and corresponding subgroup analyses for safety and efficacy will be performed as appropriate. Prior and concomitant medication, as well as exposure of investigational product, will be summarized.

Data from clinical assessments will be summarized using descriptive statistics. Numerical variables will be summarized by mean, median, standard deviation, minimum, and maximum while categorical variables will be summarized by counts and proportions.

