2.1. Primary Objective

- To assess long-term safety of weekly TransCon hGH in children with GHD previously treated in a phase 3 TransCon hGH trial

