4.2. Final Analysis

All final, planned analyses identified in this SAP will be performed after the last subject has completed the last study visit and end of study assessments, and all relevant study data have been processed and integrated into the analysis database.

5. General Statistical Considerations

All analysis will be performed based on full analysis set and summaries will be presented overall and for subjects rolling over from Study CT-301 and Study CT-302 TransCon hGH group and Genotropin group separately. Descriptive summaries will be provided where appropriate for each of the primary and secondary variables.

Continuous, quantitative (absolute values at each time point and change from baseline if applicable) variable summaries will include the number of subjects (n) with non-missing values, mean, standard deviation (SD), standard error (SE), median, minimum, and maximum, unless otherwise specified.

Categorical, qualitative, variable summaries will include the frequency and percentage of subjects who are in the particular category. In general, the denominator for the percentage calculation will be based upon the total number of subjects in the study population for the cohorts, unless otherwise specified.

All data collected on eCRF will be presented in listings.

All analysis will be performed using SAS® Software version 9.4 or later.

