8.1. Adverse Events

AE is defined as any untoward medical occurrence in a clinical investigation subject administered a pharmaceutical product and which does not necessarily have a causal relationship with the treatment. An AE can therefore be any unfavorable and unintended sign (including

abnormal laboratory finding), symptom, or disease temporally associated with the use of a medicinal (investigational) product, whether or not related to that product. An AE can arise with any use (e.g., in combination with another drug), route of administration, formulation, or dose, including an overdose.

An AE is considered treatment emergent, i.e., Treatment Emergent Adverse Event (TEAE), is any AE that was first occurred or worsened after the first dose in this extension study and before the end of study. If the AE has any missing start date, the rules stated in Section 5.2 will be applied to determine if it is treatment-emergent.

A serious AE (SAE) is SAE is any untoward medical occurrence that:

- Results in death
- Is life-threatening
- Requires inpatient hospitalization or prolongation of an existing hospitalization
- Results in persistent or significant disability/incapacity
- Is a congenital anomaly/birth defect

Summaries of incidence rates (frequencies and percentages) of individual TEAEs by MedDRA SOC and preferred term will be prepared. Such summaries will be displayed for all TEAEs, TEAEs by maximum intensity, and TEAEs by strongest relationship to study drug. In addition, related TEAE, non-related TEAE, TEAE leading to study drug discontinuation, and serious TEAE, by SOC, the preferred term and TEAE by preferred term will be also summarized. Especially, related includes definite, probable and possible relationship. Not-related includes unlikely/remote and unrelated/not related.

Each subject will be counted only once within each preferred term. If a subject experience more than one TEAE within a preferred term, only the TEAE with the strongest relationship or the maximum intensity, as appropriate, will be included in the summaries of relationship and intensity.

Data listing of AEs, TEAE leading to study drug discontinuation, serious TEAE will also be provided.

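### SAP 8.1 tabulates TEAEs only by SOC and preferred term, so no planned table gives the number of children with an hGH risk that spans several diagnoses; one prespecified grouped table would supply it

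*SAP*

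**What the plan says.** The primary objective (SAP 2.1) is: "To assess long-term safety of weekly TransCon hGH in children with GHD previously treated in a phase 3 TransCon hGH trial". The AE tables are therefore the main output of the trial.

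SAP 8.1 fixes the unit of those tables: "Summaries of incidence rates (frequencies and percentages) of individual TEAEs by MedDRA SOC and preferred term will be prepared". The further tables (maximum intensity, relationship, leading to discontinuation, serious) use the same unit. The stated rule against double counting is "Each subject will be counted only once within each preferred term". Neither document defines grouped terms or events of special interest.

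On statistics, SAP section 5 says: "Categorical, qualitative, variable summaries will include the frequency and percentage of subjects who are in the particular category". Protocol 14.4 agrees: "categorical variables will be summarized by counts and proportions". No confidence interval is planned in either document; continuous variables do get a standard error.

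Protocol 12.1.1 lists the adverse reactions known for daily hGH. Two entries plainly cover several diagnoses:

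- "Glucose intolerance, including impaired glucose tolerance/impaired fasting glucose as well as overt diabetes mellitus"
- "Fluid retention manifested by edema, arthralgia, myalgia, nerve compression syndromes (including carpal tunnel syndrome/paresthesias"

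Protocol 13 commits the sponsor to notify investigators and authorities of AEs that "Occur at a meaningfully greater frequency than described in the current" Investigator's Brochure or Reference Safety Information.

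**The concern.** A reader of the report will want to know how many children had fluid retention, or any disturbance of glucose tolerance, on long-term treatment. The planned tables do not answer that. Suppose one child has impaired glucose tolerance, another impaired fasting glucose and a third diabetes: they appear as three separate rows. Adding the rows is not valid, because a child who moved from one diagnosis to the next is in two of them. The SOC row does not help, since it also contains unrelated events.

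A small or zero count also carries no statement of precision. This matters most in the smallest parent-study group, where a printed zero is easily over-read.

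**Working it through.** **1. Planned number.** Protocol 14.2 and SAP 3.2 say the sample size follows from the prior trials. Protocol 5.3 gives about 150 for CT-301 and about 150 for CT-302: 150 + 150 = 300, the protocol's figure. The SAP's figure of about 400 does not follow from that sum, so both are used below. CT-301 was randomised 2:1, so 150 × 2/3 = 100 TransCon hGH and 150 × 1/3 = 50 Genotropin. These group sizes assume that every child rolls over.

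**2. What the planned rows leave open.** The documents give no expected AE rates, so the row counts here are assumed. With *k* rows of *r* children each, the number of distinct children lies between *r* (the same children in every row) and *k* × *r* (no overlap). Intervals are exact (Clopper-Pearson), two-sided 95%, N = 300.

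| Risk (assumed rows) | Fewest children | Most children |
|---|---|---|
| Fluid retention, 4 rows of 3 | 3/300 = 1.0% (0.21 to 2.89) | 12/300 = 4.0% (2.08 to 6.88) |
| Glucose intolerance, 3 rows of 2 | 2/300 = 0.67% (0.08 to 2.39) | 6/300 = 2.0% (0.74 to 4.30) |

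At N = 400 the fluid-retention range is 3/400 = 0.75% (0.15 to 2.18) to 12/400 = 3.0% (1.56 to 5.18). The planned tables do not say where in the range the truth lies.

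**3. Precision of a zero count.** With no events, the upper limit of the exact two-sided 95% interval is 1 − 0.025^(1/n).

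| n | Upper limit |
|---|---|
| 400 (SAP) | 0.92% |
| 300 (protocol) | 1.22% |
| 150 (CT-302) | 2.43% |
| 100 (CT-301 TransCon hGH) | 3.62% |
| 50 (CT-301 Genotropin) | 7.11% |

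**4. Why a crude percentage is not enough.** Protocol 10.1 leaves participation open-ended and lets it differ by country. Take 12 children with an event among 300. With an assumed mean follow-up of 1 year, and ignoring the stop at first event, the rate is 12/(300 × 1) = 4.0 per 100 child-years. With 2 years it is 12/(300 × 2) = 2.0. The percentage is 4.0% both times.

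**5. Which risks are affected.** Pancreatitis, slipped capital femoral epiphysis and headache are each essentially one term, and the preferred-term row already counts the children. Fluid retention and glucose intolerance are not. Intracranial hypertension is listed as a diagnosis with its accompanying signs; an isolated headache or vomiting episode is not that risk, and headache is its own entry.

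**The case against.** The strongest reply is that the protocol already limits splitting. Protocol 12.1.3 asks for a specific diagnosis or syndrome where possible and for concurrent symptoms to be put under one unifying diagnosis. That stands, and it makes several rows for one child less likely. It rests on investigator judgement, however, and falls back on the sign or symptom where there is no diagnosis. It also cannot merge different diagnoses in different children.

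Other material gives partial cover: HbA1c and thyroid values by visit (SAP 8.4), a fundoscopy listing (SAP 8.7), local tolerability in US auto-injector users (SAP 9.4) and full AE listings. None is a count of children with the risk. A count built later from listings would be labelled post hoc under SAP section 1.

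It is also fair to say that the trial is descriptive and that any reader can compute an interval from n and N. True for a single row; for a multi-term risk the numerator itself is missing.

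Further, an exact interval on a crude proportion ignores unequal follow-up. AEs that are mild and unrelated are generally not recorded, with site-level exceptions (Protocol 12.1.1, 12.1.3). Both points stand and shape the fix. A reader might infer from the table above that a zero count rules out a true risk above 1.22%. It does not: the bound applies to recorded TEAEs over the follow-up achieved.

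A reader might also take Protocol 13 as requiring a statistical comparison with the Brochure. It describes notification during ongoing review, and whether the reference documents use single or grouped terms cannot be seen here.

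**Conclusion.** The point holds for the multi-diagnosis risks in Protocol 12.1.1, clearly fluid retention and glucose intolerance. Their events can be split over rows that cannot be summed, and no planned table gives the number of children affected. In the assumed examples the gap is a factor of three to four (2 to 6 children, or 3 to 12).

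It is an inexpensive improvement to a primary-objective output, not an error. Two stronger readings are not supported. One is that none of the named risks is counted, which is wrong for single-term risks. The other is that the plan hides a safety signal: the component rows and listings remain visible, and the documents do not show how much splitting will occur.

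The sizes rest on assumed AE counts, on full roll-over for the group sizes, and on N of 300 or 400. That the components of one risk may sit in different SOCs is an assumption about the coding dictionary; the conclusion does not need it.

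**What to change.** Before the next data cut, add one table to SAP 8.1:

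- Prespecify medically reviewed term groups for the multi-term risks in Protocol 12.1.1. Build the intracranial hypertension group from diagnosis-level terms, not from isolated headache, nausea or vomiting.
- Count each child once per group. Report n (%) with an exact 95% CI, for the three parent-study groups in SAP 3.1 and overall.
- Add an exposure-adjusted rate: children with a first event divided by time at risk.
- Footnote that the figures apply to recorded TEAEs only, because AEs that are mild and unrelated are generally not collected.
- Keep the SOC and preferred-term tables, and reconcile the planned number (300 in the protocol, 400 in the SAP).

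The cost is a term list from the medical reviewer and one extra table, with no new data. The downside is that some non-specific terms, such as isolated arthralgia, will be counted, so grouped figures will look somewhat less favourable.

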8.2. Antibodies

The appropriateness of the approach taken to analyze and report anti-drug antibody data should be evaluated on a case-by-case basis [1], following recent regulatory guidance and a white paper [2]. Statistical analysis of antibodies against drug (ADA) will include (but not be limited to) the following tabulated summaries of antibody frequencies and percentages:

1. Incidence of pre-existing anti-hGH binding antibodies (positive Baseline)

2. Incidence of treatment induced anti-hGH binding antibodies by positive types (treatment emergent positive and treatment boosted positive) and overall
3. Incidence of persistent anti-hGH binding antibodies by positive types and overall
4. Incidence of transient anti-hGH binding antibodies by positive types and overall
5. Incidence of treatment induced anti-hGH neutralizing antibodies by positive types and overall
6. Incidence of persistent anti-hGH neutralizing antibodies by positive types and overall
7. Incidence of transient anti-hGH neutralizing antibodies by positive types and overall
8. Incidence of treatment induced anti-PEG antibodies by positive types and overall

In addition, treatment induced anti-hGH binding, anti-hGH neutralizing antibodies, anti-PEG antibodies will also be summarized by visit and positive types and overall.

Neutralizing antibodies are defined as confirmed binding anti-hGH antibodies that are confirmed positive in a cell-based neutralizing antibody assay.

Treatment induced ADA will include two positive types:

- Treatment emergent positive: if baseline (pre-treatment sample) is negative for ADA and post-treatment sample is positive for ADA
- Treatment boosted positive: if baseline (pre-treatment sample) is positive and post-treatment sample has a titer which is at least 4-fold higher than the pre-treatment sample.

Transient ADA is defined as treatment-induced ADA detected only at one sampling time point during study, or when there is less than 16 weeks between the first and the last ADA positive post-treatment samples.

Persistent ADA is defined as when there is more than (or equal to) 16 weeks between the first and the last ADA positive post-treatment samples.

The baseline antibody status is the status before the first dose of TransCon hGH. Therefore, for subjects from Study CT-302 and Study CT-301 TransCon hGH group, the baseline is the parent study baseline. But for subjects from Study CT-301 Genotropin group, the baseline is the extension study baseline.

In order to derive transient ADA and persistent ADA, all the data from baseline till the end of extension study will be used. In other words, for subjects from Study CT-302 and Study CT-301 TransCon hGH group, the data from parent study will be combined together with extension study data to get transient and persistent ADA status. For subjects from Study CT-301 Genotropin group, only the data from extension study will be used.

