8.2. PREMATURE SUBJECT WITHDRAWAL

Early withdrawal occurs when an enrolled subject ceases participation in the trial, regardless of the circumstances, prior to the expected completion of the trial, which in this study is until a) the product is approved and commercially available, b) the Sponsor makes alternative arrangements for continued subject access to hGH treatment, or c) treatment for pediatric growth hormone deficiency is no longer considered appropriate. Additionally, the investigator may discontinue the treatment of a subject at any time if considered to be in the subject's best interest. If treatment is permanently discontinued for any reason, trial participation should be discontinued. If the subject completes the trial or discontinues prematurely, a Completion Visit/Early Termination Visit should be performed. See Section 7.3.1 for a list of valid reasons for early termination of subjects from the trial.

For trial discontinuations, the investigator should schedule a Completion Visit/Early Termination Visit to collect data, particularly AE data reported up to 14 days after the final dose of TransCon hGH (if applicable), and to collect blood for laboratory evaluations. This visit should contain all assessments from Visit 5 (Week 52, see Schedule of Events, Section 18.2), as applicable, and will be documented in the eCRF together with the reason(s) for trial discontinuation.

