10.2. TRIAL PERIODS AND VISITS

Following confirmation of eligibility, enrolled subjects will begin attending morning visits every 13 weeks (± 2 weeks):

- **Visit 1:** Week 1 (Day 1 is the 1st weekly dose)
- **Visit 2:** Week 13 (± 2 weeks), 5 days (± 1 day) after the 11th, 12th, 13th, 14th or 15th dose
- **Visit 3:** Week 26 (± 2 weeks), 5 days (± 1 day) after the 24th, 25th, 26th, 27th or 28th dose

This pattern will continue until completion of the trial. All visits should be in the morning for consistent height measurements. Attempts should be made to adhere to the planned visit schedule. It is suggested that the site staff provide dosing, diary, and visit reminders (eg, phone calls) to subjects/parents/legal guardians/caregivers between visits, especially for those subjects who transitioned from Genotropin to TransCon hGH.

An overview of all visits is provided in the Schedule of Events (Section 18.2).

For detailed descriptions of assessments refer to Section 11.

10.2.1. Visit 1 and Day 1

Prior to any protocol related activities or evaluations, informed consent will be obtained from each potential subject in accordance with GCP and regional regulatory requirements. Informed consent may be obtained during the prior trial. The format and content of the ICF must be approved by the appropriate IRB/HREC/IEC prior to implementation. Release of medical information authorization should also be obtained at the time of informed consent.

Visit 1 of the extension trial should be the same day as the final visit of the prior trial and may occur over several days. To continue uninterrupted treatment with hGH, Day 1 (the first weekly dose) should occur on the day of Visit 1 if the subject is entering after completion of the TransCon hGH CT-301 trial (heiGHt trial), or as soon as possible thereafter. If the subject is entering after completion of the TransCon hGH CT-302 (fliGHt trial), they should remain on their dosing schedule and take their dose approximately two days after Visit 1, or as soon as possible thereafter. To accommodate extension trial activities and scheduling of procedures, the weekly dosing and visit schedule may need to be adjusted as a subject enters the extension trial. In unusual situations, a period of up to approximately 6 weeks between the final visit of the prior trial and the first dose of the extension trial is acceptable.

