10.2.5. Follow-up

Once participation in this extension trial is completed, there will be no follow-up visit except as required to follow serious adverse event (SAEs) that are determined to be related to the investigational product (See Section 12.1.3).

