5.3. Visit Window

The final visit of the parent trial should serve as the first visit (Visit 1) of the extension trial and data collected in the parent trial before the first study treatment will serve as baseline data for the extension trial. After Visit 1, subsequent visits will occur 5 days (± 1 day) post-dose at Week 13 (± 2 weeks) and then every 13 weeks (± 2 weeks) ongoing.

Post-baseline unscheduled visit (occurred after the date of initiation of the first dose) or end of study visit (early termination visit) will be mapped to the post-baseline scheduled visit with the closest target study day for each scheduled assessment according to Table 2. If the unscheduled visit is in the middle of two scheduled visits, map it to the later one. After mapping, if there are more than one visit in the same window, the visit closer to the target assessment day will be used. If more than one visit has the equal distance to the target day then the later one will be used, if more than one visit on the same day, use the time or the sequence number to select the later record. For listings and shift tables, all data points will be included.

Table 2. Analysis Window

VISIT	Week	Target Study Day	Study Day Window
Visit 1	Week 1	1	≤ 1
Visit 2	Week 13	90	2, 135
Visit 3	Week 26	181	136, 226
Visit 4	Week 39	272	227, 317
Visit 5	Week 52	363	318, 408
Visit 6	Week 65	454	409, 499
Visit 7	Week 78	545	500, 590
Visit 8	Week 91	636	591, 681
Visit 9	Week 104	727	682, 772
Visit x	Every 13 Weeks $13(x-1)$	$7*13*(x-1)-1$ if $x > 1$	Floor ($7*13*(x-1.5)$), Floor ($7*13*(x-0.5)$)-1

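### SAP 8.2 has no rule for a subject still antibody-positive at the last sample, so late-onset treatment-emergent anti-hGH ADA is labelled transient without observed resolution

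*SAP*

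**What the plan says.** SAP 8.2 splits treatment-induced anti-hGH ADA by duration, for binding antibodies (items 3 and 4) and neutralizing antibodies (items 6 and 7).

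- **Transient:** "Transient ADA is defined as treatment-induced ADA detected only at one sampling time point during study", or a first-to-last positive interval shorter than 16 weeks.
- **Persistent:** "more than (or equal to) 16 weeks between the first and the last ADA positive post-treatment samples".
- **Treatment-induced:** either emergent (negative baseline, positive afterwards) or boosted (positive baseline, and the "post-treatment sample has a titer which is at least 4-fold higher than the pre-treatment sample").
- **Data used:** "all the data from baseline till the end of extension study will be used". Parent-trial data are pooled for CT-302 and CT-301 TransCon subjects. CT-301 Genotropin subjects contribute extension data only.

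Samples are drawn at every scheduled visit (blood sample A in the Schedule of Events), at Week 13 and "then every 13 weeks (± 2 weeks) ongoing" (SAP 5.3). Protocol 8.2 says of the completion or early termination visit: "This visit should contain all assessments from Visit 5". After that, by Protocol 10.2.5, "there will be no follow-up visit except as required to follow serious adverse event" follow-up where related to the product. Nothing in SAP 8.2 mentions the result of the last available sample.

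**The concern.** A transient antibody row is naturally read as antibody that appeared and then went away. The definition does not require that. It requires only that the observed positive span be short, and a span can be short because sampling ended.

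For baseline-negative subjects the error runs one way: antibody of unknown duration goes into the more reassuring row. Long-term safety is the primary objective, antibody incidence is a safety endpoint and a secondary objective, and these items are the plan's only summary of how long an anti-hGH response lasts. With few positive subjects, one or two misplaced ones could change what the row appears to say.

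Boosted subjects raise a second question. The one-time-point limb of the transient rule speaks of treatment-induced ADA, while the persistent rule speaks of ADA-positive samples. If these are different sets of samples, one subject could carry both labels.

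**Working it through.** **1. Visit spacing.** SAP Table 2 gives target days 90, 181, 272, 363, 454, 545, 636 and 727 for Visits 2 to 9. Its formula, 7 × 13 × (x − 1) − 1, reproduces all eight. Spacing is 91 days, or 13.0 weeks, against a 16-week (112-day) cut.

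**2. Emergent ADA that stays positive to the last sample.** Rules applied literally, sampling at Visits 2 to 5:

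| First positive | Span to last sample | Label |
|---|---|---|
| Visit 2 | 39 weeks | persistent |
| Visit 3 | 26 weeks | persistent |
| Visit 4 (second-last) | 13 weeks | transient |
| Visit 5 (last) | 0 weeks | transient |

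With eight samples the result is the same: only the last two onset positions are labelled transient.

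**3. Visit windows.** Protocol 10.2 allows Visit 2 after doses 11 to 15 and Visit 3 "after the 24th, 25th, 26th, 27th or 28th dose". The gap runs from 24 − 15 = 9 to 28 − 11 = 17 weeks. Of 5 × 5 = 25 dose pairs, two give 16 weeks and one gives 17, so 3 of 25 reach the cut. Adding ± 1 day at each visit gives 25 × 9 = 225 combinations. The 17-week pair always qualifies (9), each 16-week pair qualifies in 6 of 9 (12), and a 15-week pair never does (at most 107 days): 21 of 225, or 9.3%. These are counts of permitted combinations, not probabilities. Second-last-visit onset is thus usually, but not always, transient.

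An early termination or unscheduled sample 1 or 2 weeks after a scheduled visit extends the gap in the rule to the third-last sample (13 + 1 = 14 or 13 + 2 = 15 weeks, both < 16).

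**4. Boosted ADA, both readings.** Take a baseline-positive subject who is ADA-positive at Visits 2 to 5 (39 weeks), with a titer at 4-fold or more at one visit only.

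- If the one-time-point limb counts only samples at 4-fold or more, the subject is transient (one such sample) and persistent (39 ≥ 16).
- If it counts any ADA-positive sample, the subject is persistent only.

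The SAP does not say which applies. No baseline-negative pattern over Visits 2 to 5 meets both labels.

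**5. Size.** The documents give no onset time, duration or extension incidence, so everything here is assumed. The one reference point is phase 2 of the predecessor product over 26 weeks (Protocol 5.3): 1 of 53 = 1.9%, exact 95% CI 0.05–10.1%, low titer, no neutralizing antibodies. Assumed incidence: 2–10%.

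Expected number = subjects × incidence × share of ADA-positive subjects who are unresolved yet labelled transient. The share was simulated for eight samples (104 weeks). Visits were uniform over the five dose weeks and ± 1 day. Onset was uniform, or exponential with median 13–52 weeks. Duration was exponential with median 13–52 weeks, or never resolving.

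- Lowest: 300 × 0.02 × 0.008 = 0.05.
- Highest, early-weighted onset: 300 × 0.10 × 0.132 = 4.0.
- Highest, uniform onset: 300 × 0.10 × 0.239 = 7.2.

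Hand check of the upper end: if ADA never resolves and onset is equally likely at each of 8 visits, the share is 2/8 = 25%, and 300 × 0.10 × 0.25 = 7.5. SAP 3.2 still gives 400 subjects; at that number the upper end would be 400 × 0.10 × 0.239 = 9.6.

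The same hand rule gives 2/4 = 50% with four samples and 2/12 = 17% with twelve, so the exposure falls as follow-up lengthens.

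**6. Proposed rule.** The rule under the fix was applied to every pattern of 4 and 8 samples on a 13-week grid (15 and 255 emergent; 65 and 6,305 boosted). Every pattern falls in exactly one of the three categories.

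**The case against.** The strongest reply is that little depends on the label. The analysis is descriptive and no test uses it. Neutralizing antibodies are listed for dose consideration in Protocol 9.6.2 whatever their duration. Treatment-induced ADA is tabulated by visit and all safety evaluations are listed, so a positive last sample can be found. The SAP also defines transient by observed span and never says that antibody disappeared. All of this stands and limits the importance of the point. It does not repair the row: by-visit tables and listings leave the label unchanged, and a reader of items 4 and 7 cannot tell resolved from unresolved.

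Three stronger readings are tempting and are not supported.

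- *That boosted subjects are definitely double-counted.* This needs treatment-induced ADA to mean individual samples at 4-fold or more. It can equally describe the type of subject, since the items are reported by positive type. It is an ambiguity to close.
- *That much of the transient row is unresolved.* Under the assumed onset patterns and finite median durations of 13–52 weeks, the simulated share is 17–71% with 52 weeks of sampling and 1–49% with 104 weeks. Ranges this wide reflect the assumptions, not the trial. Follow-up is open-ended, and parent data lengthen the sampling for two of the three groups.
- *That persistence should be redefined on 4-fold samples.* That would remove the overlap, but a subject boosted once who stays ADA-positive for years would move from persistent to transient, repeating the fault at issue.

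**Conclusion.** The point holds for treatment-emergent anti-hGH ADA: onset at the last visit is always labelled transient, and onset at the second-last visit is so labelled at nominal spacing, with no resolution observed. This follows from the text and the visit schedule alone. For boosted ADA the finding is only that the text allows two readings, one of which gives both labels.

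The number affected is probably small, about 0 to 7 subjects under the assumptions shown, and the neutralizing rows may be empty. It is largest where sampling is short: Genotropin switchers, early leavers, and any interim cut under SAP 4.1. Total treatment-induced incidence (items 2 and 5), anti-PEG (item 8), the by-visit tables and dosing are unaffected. The definition should be corrected because it is cheap to do so, but it does not threaten the trial's main safety conclusions.

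**What to change.** In SAP 8.2, classify the treatment-induced subjects already counted in item 2 (binding) or item 5 (neutralizing), measuring all three categories on ADA-positive post-treatment samples (for items 6 and 7, neutralizing-positive samples):

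- **Persistent:** unchanged, 16 weeks or more from first to last positive sample.
- **Transient:** less than 16 weeks from first to last positive sample, including a single positive sample, *and* an ADA-negative sample after the last positive one.
- **Unresolved at last sample:** less than 16 weeks, and the last available sample is positive. Report in its own row.

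A subject with a span of 16 weeks or more is then persistent only, which closes the boosted ambiguity without narrowing persistence, and the three rows sum to item 2 or item 5. Apply the rule at the final analysis and at any interim analysis.

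Cost: SAP wording and minor programming, with no new samples or visits. The downside is one more row per table and a somewhat lower transient count.
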